The repeated measures logistic regression model will include the following covariates (with example variable names): treatment (ptrtcd), period baseline FEV ₁ (pbli), sex (sex), age (age), treatment period (pernum) and smoking history (supkyr: number of pack years) as fixed effects. A SAS procedure of the following structure will be used:

Statistical Analyses

```
proc genmod data=start descending ;
  class ptrtcd sex pernum subjid / param=ref ;
  model binv = ptrtcd pernum pbli age sex supkyr / dist=bin ;
  repeated subject=subjid / type=unstr corrw;
  estimate "logit FF/VI Vs FP" ptrtcd 1 / exp ;
  ods output Estimates=GEE_or_est ;
run ;
```

Where binv is the binary variable that takes the value 1 if at the given post-challenge time point a subject has an FEV₁ measurement that is $\geq 95\%$ of their pre-exercise FEV₁ measurement and 0 otherwise.

The above code specifies a repeated measures logistic regression model where parameters are estimated using the Generalized Estimating Equation (GEE) method. GEE uses a “working” covariance matrix to model the within-subject dependences during estimation but calculates parameter estimator standard errors using an empirical estimate of the within-subject covariance matrix.

The “estimate” statement estimates the odds ratio of FF/VI compared to FP with 95% confidence limits which are displayed in the SAS output in the “L’Beta Estimate” and “L’Beta Confidence Limits” columns using the “Exp(logit FF/VI Vs FP)” row - these can be found in the “GEE_or_est” dataset produced by the “ods output” statement in the “LBetaEstimate” and “LBetaLowerCL/LBetaUpperCL” columns using the entry in row 2. Note that the quantity displayed in the SAS output in the “Mean Estimate” column is the inverse logit of the FF/VI estimate which is not equal to the odds ratio of FF/VI relative to FP.

Model Checking & Diagnostics

- Refer to [Appendix 11](#): Model Checking and Diagnostics for Statistical Analyses.

Model Results Presentation

- The estimated treatment difference will be displayed as an odds ratio together with the 95% CI and p-value for the treatment comparison along with the number and percentage of subjects in each category. The adjusted treatment ratio and 95% confidence interval will be plotted.

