The repeated measures ordinal multinomial regression model will include the following covariates (with example variable names): treatment (ptrtcd), period baseline FEV ₁ (pbli), sex (sex), age (age), treatment period (pernum) and smoking history (supkyr: number of pack years) as fixed effects. A SAS procedure of the following structure will be used:

Statistical Analyses

```

proc genmod data=start descending ;
  class ptrtcd sex pernum subjid / param=ref ;
  model catv = ptrtcd pernum pbli age sex supkyr
    / dist=multinomial ;
  repeated subject=subjid / type=ind corrw ;
  estimate "logit FF/VI Vs FP" ptrtcd 1 / exp ;
  ods output Estimates=GEE_or_estm ;
run ;

```

Where catv is the multinomial variable that takes the value 1, 2 or 3 if a subject has a post-exercise minus pre-exercise FEV₁ value, denoted by X, of -10 < X, -20 < X ≤ -10, or X ≤ -20 respectively.

The above code specifies a repeated measures ordinal multinomial regression model where parameters are estimated using the Generalized Estimating Equation (GEE) method. GEE uses a “working” covariance matrix to model the within-subject dependences during estimation but calculates parameter estimator standard errors using an empirical estimate of the within-subject covariance matrix. The multinomial regression model assumes proportional odds, that is, the odds ratio of catv ≤ 1 for FF/VI compared to FP is the same as the odds ratio of catv ≤ 2 for FF/VI compared to FP. Thus it is assumed there is a single true odds ratio of catv being in an equal or lower category than j, for j=1, 2 (henceforth referred to simply as the odds ratio).

The “estimate” statement estimates the odds ratio of FF/VI compared to FP with 95% confidence limits which are displayed in the SAS output in the “L’Beta Estimate” and “L’Beta Confidence Limits” columns using the “Exp(logit FF/VI Vs FP)” row - these can be found in the “GEE_or_est” dataset produced by the “ods output” statement in the “LBetaEstimate” and “LBetaLowerCL/LBetaUpperCL” columns using the entry in row 2. Note that the quantity displayed in the SAS output in the “Mean Estimate” column is the inverse logit of the FF/VI estimate which is not equal to the odds ratio of FF/VI relative to FP.

Model Checking & Diagnostics

- Refer to [Appendix 11](#): Model Checking and Diagnostics for Statistical Analyses.

Model Results Presentation

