- The estimated treatment difference will be displayed as an odds ratio together with the 95% CI and p-value for the treatment comparison along with the number and percentage of subjects in each category. The adjusted treatment ratio and 95% confidence interval will be plotted.
- The analysis will also be performed for the percentage of subjects who demonstrate a decrease from pre-exercise challenge FEV₁ following the exercise challenge at 23 hours post evening dose on day 1 of the treatment period.

7.2.2.5. Maximal Percent Decrease from Treatment Period Baseline FEV₁, Following Exercise Challenge at 12 Hours and 23 Hours Post Evening Dose at the End of the 2-Week Treatment Period

Statistical Analyses
Endpoint(s)

 Maximal percent decrease from treatment period baseline FEV₁ following exercise challenge at 12 hours and 23 hours post evening dose at the end of the 2-week treatment period
Populations

 These analyses will be performed on the Intent-to-Treat (ITT) populations
Model Specification

This endpoint will be analysed using a model of the same structure as described for the primary endpoint in Section 7.1.2.
 
An analysis of the change from period baseline in each of the individual serial FEV₁ measurements will be performed separately (by their planned time). In each case the analysis will use a model of the same structure as described for the primary endpoint in Section 7.1.2.

Model Checking & Diagnostics

 Refer to Appendix 11: Model Checking and Diagnostics for Statistical Analyses.
Model Results Presentation

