10.5. Appendix 5: Data Display Standards & Handling Conventions

10.5.1. Study Treatment & Sub-group Display Descriptors

Treatment Group Descriptions			
RandAll NG		Data Displays for Reporting	
Code	Description	Description	Order [1]
A	FF/VI 100/25mcg OD	FF/VI 100/25 OD	1
B	FP 250mcg BD	FP 250 BD	2

NOTES:

1. Order represents treatments being presented in TFL, as appropriate.

If a subject attends at least one scheduled clinic visit for a treatment period, then they will be counted as having taken part in that treatment period and will contribute to the population numbers (i.e. “Big N” numbers) for the treatment that they were randomized to receive in that period.

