Where minimum post-exercise FEV ₁ is defined in the same way as for the primary endpoint and the same minimum number of non-missing FEV ₁ values are required for the endpoint to be calculated.
Proportion of Subjects With a Post-Challenge FEV₁ No More Than 5% Lower Than Their Pre-Exercise FEV₁
Subjects meeting the criteria will be those who had a post-challenge FEV ₁ \geq 95% of their pre-exercise FEV ₁ . For the time point in question, each subject's post-challenge FEV ₁ as a percentage of their pre-exercise FEV ₁ will be derived as follows:
$\frac{\text{Post Exercise FEV}_1}{\text{Pre-Exercise FEV}_1} \times 100$
If this number is \geq 95% then the subject will have met the criteria.
% of Subjects with a Decrease from Pre-Exercise FEV₁ in 3 Categories
For the time point in question, each subject's percentage decrease from pre-exercise FEV ₁ will be derived as follows:
$\frac{\text{Pre-Exercise FEV}_1 - \text{Post Exercise FEV}_1}{\text{Pre-Exercise FEV}_1} \times 100$
Subjects will then be allocated to one of the 3 categories.
Weighted Mean 0-60 Minutes for % Decrease from Pre-Exercise FEV₁ Following Exercise Challenge
For each time point, the percentage decrease from pre-exercise FEV ₁ will be derived as follows:
$\frac{\text{Pre-Exercise FEV}_1 - \text{Post Exercise FEV}_1}{\text{Pre-Exercise FEV}_1} \times 100$
The weighted mean will then be calculated as the average area under the curve (AAUC) using the trapezoidal rule, and dividing by the relevant time interval. The 0 minute value, coming from the pre-exercise measurement, will be 0 by definition and actual times will be used for all other measurements in the calculation of the AAUC.
The AAUC will be calculated from the first non-missing time point to the last non-missing time point. If one or more observations are missing between two non-missing observations, the value(s) will be linearly interpolated between the two non-missing values.
The AAUC ($t_0 - t_L$ mins) will be calculated as follows:

Secondary and Other Endpoints

$$\text{AAUC}_{(t_0-t_L \text{ mins})} = \frac{\frac{1}{2} \sum_{i=0}^{L-1} (C_i + C_{i+1})(t_{i+1} - t_i)}{t_L - t_0}$$

Where,

i = collected measurement

L = last collected measurement

C_i = result of collected measurement i

t_i = actual time of assessment for collected measurement i

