6. If 5 is significant then test at the 5% level the null hypothesis that the true population difference between the treatment group means in weighted mean 0-60 minutes for percentage decrease from pre-exercise FEV₁ following the exercise challenge at 23 hrs post-dose at the end of the 2-week treatment period is zero.

If either the gatekeeper hypothesis or any of the other above null hypotheses are not rejected, then although all of the subsequent analyses will still be performed, the results and the associated p-value, will be used for descriptive purposes only.

The treatment comparisons defined as part of the multiple testing strategy will be limited to the specified key comparisons above. Other pairwise comparisons will be performed, but will not form part of the multiple testing strategy. Analyses of other efficacy measures for the FF/VI versus FP treatment comparison are nested under the secondary efficacy measures and no multiplicity adjustment is planned for these other efficacy endpoints.

If significance is achieved for the FF/VI versus FP treatment comparison on the primary efficacy endpoint, then the secondary endpoints will be tested in a closed-testing manner using the hierarchy of comparisons. If significance is also achieved for each of the secondary efficacy endpoints, then all other efficacy endpoints will be tested for the FF/VI versus FP treatment comparison without further multiplicity adjustment.

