10.13.4. Efficacy Figures

Efficacy: Figures		
No.	Population	Title
Primary Endpoint		
2.1.	ITT/PP	Adjusted Treatment Differences for Maximal Percent Decrease from Pre-Exercise FEV1 Following Exercise Challenge
2.2.	ITT (15 Years or Older)	Adjusted Treatment Differences for Maximal Percent Decrease from Pre-Exercise FEV1 Following Exercise Challenge - ITT (15 Years or Older)
Secondary and Other Endpoints		
2.3.	ITT	Adjusted Treatment Differences for Maximal Decrease from Pre-Exercise FEV1 (L) Following Exercise Challenge - Intent-to-Treat
2.4.	ITT (15 Years or Older)	Adjusted Treatment Differences for Maximal Decrease from Pre-Exercise FEV1 (L) Following Exercise Challenge - ITT (15 Years or Older)
2.5.	ITT	Adjusted Treatment Differences for Maximal Percent Decrease from Period Baseline FEV1 Following Exercise Challenge
2.6.	ITT	Adjusted Treatment Differences for Maximal Decrease from Period Baseline FEV1 (L) Following Exercise Challenge
2.7.	ITT	Adjusted Mean Change from Period Baseline in Individual Serial FEV1 Measurements (L) - Intent-to-Treat
2.8.	ITT (15 Years or Older)	Adjusted Mean Change from Period Baseline in Individual Serial FEV1 Measurements (L) - ITT (15 Years or Older)
2.9.	ITT	Adjusted Treatment Ratios for Proportion of Subjects with a Post-Challenge FEV1 No More Than 5% Lower Than Pre-Exercise FEV1 - Intent-to-Treat
2.10.	ITT (15 Years or Older)	Adjusted Treatment Ratios for Proportion of Subjects with a Post-Challenge FEV1 No More Than 5% Lower Than Pre-Exercise FEV1 - ITT (15 Years or Older)
2.11.	ITT	Adjusted Treatment Differences for Weighted Mean 0-60 min for Percentage Decrease from Pre-Exercise FEV1 Following Exercise Challenge - Intent-to-Treat
2.12.	ITT (15 Years or Older)	Adjusted Treatment Differences for Weighted Mean 0-60 min for Percentage Decrease from Pre-Exercise FEV1 Following Exercise Challenge - ITT (15 Years or Older)
2.13.	ITT	Adjusted Treatment Ratios for Percentage of Subjects with a Decrease from Pre-Exercise FEV1 in 3 Categories
2.14.	ITT	Adjusted Treatment Differences and Ratios for ACQ-5 Endpoints at Day 14
Forest Plot Across Endpoints		
2.15.	ITT	Adjusted Treatment Differences and Ratios for Primary and Secondary Efficacy Endpoints at Day 14 - Intent-to-Treat
2.16.	ITT (15 Years or Older)	Adjusted Treatment Differences and Ratios for Primary and Secondary Efficacy Endpoints at Day 14 - ITT (15 Years or Older)

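### SAP 7.2.2.4: with FP as reference, the DESCENDING option makes the ordinal model return the odds ratio of a larger FEV₁ fall, the reciprocal of the odds ratio the text defines

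*SAP*

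**What the plan says.** SAP 7.2.2.4 specifies a proportional-odds GEE model for catv, which takes the values 1, 2 and 3 for falls of under 10%, 10% to under 20%, and 20% or more. A higher code is a worse outcome. The text then names its estimand: "it is assumed there is a single true odds ratio of catv being in an equal or lower category than j", for FF/VI compared with FP. The code above that text opens with "proc genmod data=start descending", uses reference-cell coding (`param=ref`) with no reference level named, and exponentiates +1 times the treatment coefficient. No sentence inverts the result.

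The binary recovery model in SAP 7.2.2.2 uses the same three devices. There the response is described as follows: "Where binv is the binary variable that takes the value 1 if at the given post-challenge time point" the subject's FEV₁ is at least 95% of the pre-exercise value. The higher code is therefore the good outcome.

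The treatment table in SAP 10.5.1 lists code A, "FF/VI 100/25mcg OD", first and FP as code B, second. It does not give the values of ptrtcd. The results go to Table 2.31, with the odds ratio shown "along with the number and percentage of subjects in each category", and to Figure 2.13, titled "Adjusted Treatment Ratios for Percentage of Subjects with a Decrease from Pre-Exercise FEV1 in 3 Categories". SAP 10.10.1 says that "no multiplicity adjustment is planned for these other efficacy endpoints".

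**The concern.** DESCENDING has the same mechanical effect in both models: it makes the higher response code the event. In the recovery model that is what the text wants. In the ordinal model it is the opposite, because the text defines the odds ratio for the lower codes. The explanatory paragraph in 7.2.2.4 is close to that of 7.2.2.2 and refers to the binary model's output dataset (GEE_or_est), although the ordinal code writes GEE_or_estm. This suggests, as an inference only, that the binary template was reused without changing its direction.

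A protective effect of FF/VI would then be printed as an odds ratio below 1 under a definition by which protection should exceed 1. This would apply to every run of the model: the 12-hour and 23-hour challenges at the end of treatment, and the 23-hour challenge on day 1. It would also point the opposite way from the recovery ratios in Figure 2.9.

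**Working it through.** The documents give no figure for this odds ratio, so there is none to reproduce. The check has three parts.

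**1. What each model estimates**

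A cumulative-logit model fits logit P(Y in the first j ordered levels) = a_j + x′β. With DESCENDING the order is 3, 2, 1, so the modelled probabilities are P(catv = 3) and P(catv ≥ 2). No link is stated; the cumulative logit is taken from the text's proportional-odds description and the logit label on the ESTIMATE line. With `param=ref` and no `ref=`, the last level is the reference. That is FP if ptrtcd sorts in the A, B order of SAP 10.5.1, which the FF/VI-versus-FP label on the ESTIMATE line also supports.

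| Reference level | Recovery model (7.2.2.2) returns | Ordinal model (7.2.2.4) returns |
|---|---|---|
| FP | FF/VI v FP, recovered: agrees with text | FF/VI v FP, larger fall: reciprocal of text |
| FF/VI | FP v FF/VI, recovered: reciprocal of text | FP v FF/VI, larger fall = FF/VI v FP, smaller fall: agrees with text |

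If ptrtcd is coded alike in both models, exactly one odds ratio contradicts its text, whichever treatment is the reference.

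**2. Arithmetic illustration (assumed shares)**

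- Assume FP shares of 30/30/40% for catv 1/2/3. The cumulative probabilities are 0.30 and 0.60, so the odds are 0.4286 and 1.5.
- Assume a true odds ratio of 2 for a smaller fall. The FF/VI odds are 0.857 and 3.0, the cumulative probabilities 0.4615 and 0.75, and the shares 46.2/28.8/25.0%.
- Odds ratio as the text defines it: 0.857/0.4286 = 3.0/1.5 = 2.00.
- Odds ratio as the code targets it, catv ≥ 2: (0.5385/0.4615)/(0.70/0.30) = 0.50. For catv = 3: (0.25/0.75)/(0.40/0.60) = 0.50.
- In simulated sets of 56 subjects, the median robust SE of the log odds ratio was 0.278 at an assumed latent within-subject correlation of 0.5. The interval is 2 × exp(±1.96 × 0.278) = 1.16 to 3.45, which the code would show as 0.29 to 0.86. Either way z = ln 2/0.278 = 2.49 and p = 0.013.
- At correlations of 0.3 and 0.7 the SEs were 0.312 and 0.236. The intervals are about 1.1 to 3.7 and 1.3 to 3.2, shown as 0.27 to 0.92 and 0.31 to 0.79.

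**3. Simulated crossovers fitted in both response orders**

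From SAP 2.5: 56 subjects, a 5-point difference in favour of FF/VI, within-subject SD 8. Assumed: between-subject SD 8, and a mean FP fall of 15, 20 or 25%. One dataset per row was fitted with independence working correlation and empirical SEs, with treatment and period as the only covariates.

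| Mean FP fall | DESCENDING, as written | Default order | p (both) |
|---|---|---|---|
| 15% | 0.61 (0.36–1.03) | 1.64 (0.97–2.79) | 0.066 |
| 20% | 0.46 (0.28–0.77) | 2.15 (1.30–3.57) | 0.003 |
| 25% | 0.53 (0.29–0.96) | 1.90 (1.04–3.45) | 0.036 |

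FF/VI is truly better in every row; the true odds ratios of a smaller fall are about 2.0 to 2.3. The code as written returns the reciprocal each time.

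**The case against.** The strongest counter-argument is that the reversal of this particular model is conditional. SAP 10.5.1 gives randomisation codes and display order, not ptrtcd values, so FP as reference is probable rather than documented. That stands, and the conclusion is worded accordingly. It does not clear the plan, because the other coding moves the reversal to the recovery odds ratios, which at 30 minutes are steps 2 and 4 of the hierarchy in SAP 10.10.1.

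Second, the harm depends on labels that cannot be seen. The display shells are in separate documents (SAP 10.14), the code is offered only as a structure, and a QC tracker is mentioned in SAP 10.5.3. Category percentages beside the odds ratio would help expose a wrong sign in the table. All of this makes detection more likely, but it does not reconcile the code with the definition.

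Third, the title of Figure 2.13 names a decrease, so a reader might take an odds ratio below 1 as fewer or smaller falls and reach the right conclusion. That is fair. But the three categories include the favourable one, the title states no direction, and the SAP's own definition says the opposite. Pointing the other way from the recovery ratios would be harmless if the larger-fall odds ratio were declared as such.

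Finally, the reciprocal is an algebraic identity and the numerical sizes rest on assumed shares and correlations. Both are true; the numbers show scale only.

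**Conclusion.** The concern holds. The code and the definition in SAP 7.2.2.4 disagree if FP is the reference level, and nothing in the SAP inverts the estimate. An odds ratio of 2.00 would be reported as 0.50, with the confidence limits inverted too. This assumes that the code is run as written, that the output is labelled by the SAP text, that the link is the cumulative logit, and that ptrtcd puts FP last.

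The effect is limited to direction. Model fit and p-value are unchanged, the exact correction is a reciprocal, and the primary analysis is untouched. The hierarchical tests are also unaffected: under the alternative coding, the recovery odds ratio would change direction but its p-value would not. It should still be corrected before unblinding, because SAP 10.10.1 allows the other endpoints to be tested if every secondary test succeeds, and a significant result could then carry the wrong direction.

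**What to change.** 1. Remove DESCENDING from the multinomial call in 7.2.2.4 only, and keep it in the binary model. Alternatively, keep it and redefine the reported odds ratio as that of an equal or higher category, that is, of a larger fall.
2. In both models name FP as the reference for ptrtcd with `ref=` on the CLASS statement.
3. State in Table 2.31 and Figure 2.13 which direction favours FF/VI.

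Three wording corrections belong in the same edit, although they do not bear on the reversal. X in 7.2.2.4 is described as a plain post-minus-pre difference and should use the percentage formula of SAP 10.6.3. That section says "Subjects will then be allocated to one of the 3 categories" but leaves open which post-exercise value decides the category. The dataset names GEE_or_estm (code) and GEE_or_est (text) should agree.

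The cost is one word of code, one CLASS option in each model and a few lines of SAP text, with no new data and no effect on the primary or secondary tests.

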7.2.2.6. ACQ-5 Score at the End of the 2-Week Treatment Period

Statistical Analyses
Endpoint(s)

 Change from baseline in Asthma Control Questionnaire-5 (ACQ-5) score at the end of the 2-week treatment period Percentage of subjects controlled, defined as an ACQ-5 score ≤ 0.75, at the end of the 2-week treatment period Percentage of subjects achieving an improvement of ≥ 0.5 in ACQ-5 score at the end of the 2-week treatment period
Populations

 These analyses will be performed on the Intent-to-Treat (ITT) populations

Statistical Analyses
Model Specification

For the change from period baseline analysis, a mixed model repeated measures (MMRM) model will include the following covariates (with example variable names): treatment (ptrtcd), sex (sex), age (age), treatment period (pernum), smoking history (supkyr: number of pack years), period baseline ACQ-5 score (pbli) and the mean of the two period baseline ACQ-5 scores (mpbli) as fixed effects, and a random intercept for each subject (subjid). A SAS procedure of a similar structure to that shown for the primary endpoint in Section 7.1.2 will be used.
 
For both of the binary endpoints, a repeated measures logistic regression model will include the following covariates (with example variable names): treatment (ptrtcd), sex (sex), age (age), treatment period (pernum), smoking history (supkyr: number of pack years), period baseline ACQ-5 score (pbli) as fixed effects. A SAS procedure will be used that is of a similar structure to that shown in Section 7.2.2.2 for the secondary endpoint of the proportion of subjects with a 30 minute post-challenge FEV₁ that was no more than 5% lower than their pre-exercise FEV₁ following the exercise challenge at 12 hours and 23 hours post evening dose at the end of the 2-week treatment period.

Model Checking & Diagnostics

 Refer to Appendix 11: Model Checking and Diagnostics for Statistical Analyses.
Model Results Presentation

 For the change from period baseline analysis, the adjusted means for each treatment and the estimated treatment difference for the treatment comparison will be presented together with a 95% confidence interval for the difference and a p-value. The adjusted treatment difference and 95% confidence interval will be plotted. For both of the binary endpoints, the estimated treatment difference will be displayed as an odds ratio together with the 95% CI and p-value for the treatment comparison along with the number and percentage of subjects in each category. The adjusted treatment ratio and 95% confidence interval will be plotted.

